# TRIAL EVALUATION PROTOCOL: STRENGTHENING FAMILIES, PROTECTING CHILDREN - FAMILY SAFEGUARDING MODEL

Intervention Developer	Hertfordshire County Council
Evaluator	What Works for Children's Social Care
Principal Investigator	[name]
Protocol Author(s)	[name] (RCT lead), [name] (IPE lead), [name], [name], [name], [name]
Type of Trial	Stepped Wedge Cluster Randomised Controlled Trial (RCT) & Implementation and Process Evaluation (IPE)
Age or Status of Participants	RCT: Children aged 0 - 12, that have been referred to Children's Social Care (further restrictions apply depending on outcome measure) IPE: Staff in Children's/Family Safeguarding Teams, and Families including children aged 0-12 who are referred to and supported by Children's/Family Safeguarding Teams.
Number of Participating Local Authorities	5
Number of Children and Families	RCT: 51,000
Primary Outcome(s)	RCT: Likelihood of becoming looked after
Secondary Outcome(s)	RCT: Likelihood of returning to statutory services following a closed CPP; CPP plan duration; days on CPP; likelihood of proceedings to care proceedings likelihood of repeat referrals for domestic violence; mental health, or substance misuse; unauthorised school absence rates.
Contextual Factors	Local authorities had to apply to be part of the Innovation Programme. Participation in the programme required an Ofsted rating of "requires improvement" and high rates and/or rising numbers of looked after children over the last three years.

## Background

### Strengthening Families, Protecting Children

This evaluation is part of Strengthening Families, Protecting Children (SFPC), a five-year Department for Education funded programme supporting 18 local authorities to improve work with families and safely reduce the number of children entering care. SFPC will support selected local authorities to adapt and adopt one of three [children's social care innovation programme](#) projects in their own area.

The three projects are:

- Leeds Family Valued
- Family Safeguarding Hertfordshire
- North Yorkshire's No Wrong Door

What Works for Children's Social Care (WWCSC) is conducting a three-part evaluation for each model:

- A **pilot evaluation** in one 'Trailblazer' local authority (LA). This local authority is the first in this evaluation to implement to model.
- This is followed by an **impact evaluation** of the model in five subsequent local authorities, with a stepped wedge cluster Randomised Controlled Trial (RCT) design.
- This is accompanied by an **Implementation and Process Evaluation (IPE)** across these same five local authorities, to understand the delivery during the rollout of the model.

This document sets out the protocol for the impact evaluation and IPE parts of the evaluation of Family Safeguarding.

### Family Safeguarding

The Family Safeguarding Model was developed in Hertfordshire with support from the Department for Education's Innovation Programme. Its delivery in Hertfordshire was evaluated by academics at Cardiff and Bedfordshire Universities.

The intervention supports a whole-system change to a local authority's child protection approach for children up to adolescence, focusing on supporting the needs of children and adults in order that children can safely remain within their families. This involves:

- Establishing multi-disciplinary teams where specialist adult practitioners in domestic abuse, mental health and substance misuse are co-located with social workers under a unified management structure. This enables a multi-disciplinary whole family response through direct assessment and support from specialist adult practitioners as well as multi-professional group case discussions and sharing of knowledge and skills across disciplines.

---

- Use of Motivational Interviewing (MI) as a framework for practice for all staff. Staff undergo training and ongoing skills development workshops and follow a structured solution-focussed intervention programme with families which aims to work collaboratively with families and increase engagement.
- Using an electronic assessment workbook which provides a single data tool for all professionals and links to the work programme. This increases ease of information sharing between professionals and reduces social worker time spent recording and sharing information.

Social workers trained in Motivational Interviewing may see wider benefits to their practice. However, the full Family Safeguarding package, i.e. the involvement of adult specialist practitioners, is primarily expected to support cases where the primary referral reasons relate to child abuse or neglect from within the family. The model developers also recommend that this Family Safeguarding work is facilitated where cases with contextual safeguarding or other non-family based risk factors are held by separate teams (sometimes called Adolescent Teams). Although this is the preferred approach, local variation in system structure may mean that this preferred structure is not always possible. However even in teams with a wider remit the core Family Safeguarding work would still take place primarily where safeguarding risks come from within the family.

A draft logic model setting out the contextual facilitators and barriers, interventions, mechanisms and outcomes for the Family Safeguarding Model is available in Appendix A. The logic model is based on programme theory and not on prior evidence of impact. The logic model will be subject to refinement following completion of the pilot evaluation in Summer 2020.

Although terminology will vary in each authority, throughout this protocol, ‘children’s safeguarding teams’ is used to refer to social work teams undertaking safeguarding and child protection functions before the introduction of the family safeguarding model, while ‘family safeguarding teams’ is used to refer to these such teams after the introduction of the family safeguarding model.

## Context

The IPE and RCT parts of the evaluation will be undertaken in the local authorities funded by the Department for Education to introduce Family Safeguarding as part of the Strengthening Families, Protecting Children programme, with the exception of the Trailblazer who is participating in a separate pilot evaluation. These local authorities are due to launch Family Safeguarding at six-month intervals beginning in April 2020. In the order they will be rolled out, these local authorities are Walsall, Lancashire, Telford & Wrekin, Wandsworth and Swindon.

All authorities had a judgement of ‘requires improvement to be good’ at the point at which they applied for the programme. However, at the point of rollout to the first local authority, Children’s Services in three of these authorities (Walsall, Lancashire and Wandsworth) have an Ofsted judgement of ‘requires improvement to be good’, while Swindon received a

judgement of 'good' in July 2019 and Telford & Wrekin received a judgement of 'outstanding' in January 2020. These authorities were selected by the Department for Education to participate in the programme due to having high rates of children looked after compared to their local authority statistical neighbour median over the last 3 years, and/or rising rates of children looked after in each of the last 3 years.

York Consulting is currently conducting a process evaluation of Family Safeguarding in four additional local authorities, namely Peterborough, Luton, Bracknell Forest and West Berkshire.

## Impact Evaluation

### Aims

Family Safeguarding was first implemented in Hertfordshire and demonstrated promising results. However, the original evaluation was conducted using a pre-post design. The current evaluation uses a Stepped Wedge Cluster Randomised Controlled Trial design to provide a more robust evaluation of the impacts of Family Safeguarding when scaled to five other local authorities and provide an estimate of the impact on children and families on key outcomes.

### Research questions

While the Family Safeguarding model is a whole system reform that aims to affect multiple parties engaged with Children's Services, the key measure of the programme's success used in this impact evaluation, is whether it achieves one of its primary goals - namely reducing the number of children looked after. The population of interest are children who have been referred to children's social care and are under the age of 13 at the time of referral. This is the primary age group that the Family Safeguarding teams in the developer local authority Hertfordshire work with and is designed to impact. While Safeguarding teams can in theory work with adolescents as well, safeguarding concerns among adolescents are more likely to become contextual which in some local authorities are specifically addressed by adolescent teams. We assess the following primary research question of interest:

1. What is the impact of Family Safeguarding on the likelihood of children becoming looked after?

Given the multifaceted nature of the model, we also expect to see changes in other important, but secondary outcomes, such as a reduction in the likelihood of children returning to statutory services. For some of these secondary outcomes our population of interest is either expanded, or further restricted, as detailed in the RCT Design Table below. To provide a more thorough assessment of the model's impacts, we address the following secondary research questions:

---

 The process and impact evaluation conducted by York Consulting includes a series of case studies and interviews and a cost-benefit analysis using a Fiscal Return on Investment model.

2. What is the impact of Family Safeguarding on the likelihood of children having a CPP closed then returning to statutory services?
3. What is the impact of Family Safeguarding on the time spent on child protection plans?
4. What is the impact of Family Safeguarding on the likelihood of a case progressing from pre-proceedings (under the PLO) to care proceedings?
5. What is the impact of Family Safeguarding on the likelihood of children being re-referred for parental substance misuse, domestic violence or parental mental health issues?
6. What is the impact of Family Safeguarding on the unauthorised school absence rates of children referred to children's social care?

## Design

The study design of the impact evaluation is a cross-sectional stepped-wedge cluster randomised controlled trial, where the timing of implementation is staggered across local authorities. The point at which local authorities begin implementing the intervention is selected at random, constrained by their level of readiness to implement the model. In this way, all the local authorities in the sample will eventually implement the Family Safeguarding model, but randomising the start date of the implementation of Family Safeguarding will allow service users in the local authorities that have not yet implemented the programme to act as a control group against service in local authorities where Family Safeguarding has already been implemented.

Given that, prior to the evaluation, there was already an existing need to stagger roll-outs over time, this means that nobody will be denied a service that they might otherwise have received. Local authorities implementing on different timescales will also allow us to take time-based effects into account, with every local authority also acting as a control group for itself over time.

RCT Design Table		
Trial type and number of arms		Stepped wedge cluster randomised controlled trial, two arms
Unit of randomisation		Local authority
Stratification variables		Low/High readiness to implement
Primary outcome	variable	Whether or not the child has become looked after
	measure	Coded 1 if the child has become looked after at any point within 18 months of the referral. Coded 0 if the child has not become looked after within this period.
	sample	Children aged 0-12 that have been referred within the trial period.

Secondary outcome 1	variable	Whether or not the child has returned to statutory services, following a CPP
	measure	Coded 1 if the child finishes a CPP and then returns to statutory services (i.e. begins a new CPP, CIN plan or becomes CLA) within 36 months of the referral start date, coded 0 if they have not re-entered statutory services within this time period.
	sample	Children aged 0-12 that have been referred within the trial period without them going into care.
Secondary outcome 2	variable	CPP plan duration
	measure	Discrete variable equal to the number of days that the child has been on a single CPP. Plan length is recorded up to 24 months from the start of the CPP and censored for larger values.
	sample	Children aged 0-12 that have been referred within the trial period and that also started a CPP plan within 12 months of the initial referral start date.
Secondary outcome 3	variable	Days on CPPs
	measure	Discrete variable equal to the number of days that the child has been on CPP plans over a period of 36 months from initial referral.
	sample	Children aged 0-12 that have been referred within the trial period.
Secondary outcome 4	variable	Whether or not the child proceeds to care proceedings
	measure	Coded 1 if the child has started care proceedings following pre-proceedings (under the PLO) within 16 weeks of the first pre-proceedings meeting, and coded 0 if not.
	sample	Children aged 0-12 that have been referred within the trial period and that started pre-proceedings within 18 months of the referral.
Secondary outcome 5	variable	Repeat referrals for parental substance misuse, parental mental health or domestic violence
	measure	Coded 1 if the child has been re-referred within 18 months of an initial referral where the factors identified at the end of assessment included either parental substance misuse, parental mental health, or domestic violence. As measured 18 months after first referral. Coded 0 if not re-referred within 18 months.
	sample	Children aged 0-12 that have been referred within the trial period. The factors identified at assessment must include parental substance misuse, domestic violence, or parental mental health.

Secondary outcome 6	variable	Unauthorised school absence rates
	measure	Continuous variable equal to the percentage of sessions missed due to unauthorised absence out of all the school sessions the child was expected to attend for the three terms that start after the initial referral date.
	sample	Children aged 0-12 that have been referred within the trial period.

We will use administrative, secondary data for the analysis. The administrative data will be provided by each local authority in the evaluation. Local authorities that are participating in the evaluation have committed to providing data. For details please see the Data Gathering section below.

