## Outcome measures

For the trial we will evaluate one primary outcome measure and six secondary outcome measures. Individual level data will be collected directly from the five local authorities participating in the Family Safeguarding trial, detailed above. Below we give an explanation

and rationale of the outcomes outlined in the RCT Design Table. In the instance of any unintentional inconsistencies, the above table definitions should take precedent in the analysis.

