#### **Whether or not the child has returned to statutory services, following a CPP**

To answer research question 2, we use a binary outcome measure, indicating whether or not the child has returned to statutory services within 36 months of the initial referral start date, having had a CPP closed following the initial referral start date. Our sample will include any child aged 0-12 that has had a referral within the trial period.

This outcome will seek to act as a measure for the quality of assessment and direct work with children and their families. We choose return to statutory services (rather than considering CPPs only) as our outcome measure to avoid classifying children whose needs have escalated to e.g. going into foster care as "non-returners". We acknowledge that we do count children that stay on CPPs as non-returners. If implementing Family Safeguarding changes the allocation of children to CIN and CP plans, this will further affect the measure. Thus care must be taken interpreting this outcome measure.

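### Secondary outcome 1: the governing table drops children who go into care, although its own measure counts becoming looked after as a return and the narrative keeps all referred children

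*Protocol*

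**What the plan says.** The RCT Design Table (Protocol, Design) defines secondary outcome 1 in two lines that do not fit together. The measure codes 1 for a child who, after completing a CPP, "returns to statutory services (i.e. begins a new CPP, CIN plan or becomes CLA) within 36 months of the referral start date". The sample line directly below it is "Children aged 0-12 that have been referred within the trial period without them going into care". No time window is attached to the exclusion.

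The narrative for the same outcome (Outcome measures, return to statutory services following a CPP) gives a different sample: "Our sample will include any child aged 0-12 that has had a referral within the trial period". It also explains the broad definition of return, which was chosen to "avoid classifying children whose needs have escalated to e.g. going into foster care" as children who did not return. Footnote 4, attached to this outcome, says that the clock starts at referral in order to limit endogeneity from selection into the sample.

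The opening of Outcome measures settles conflicts between table and narrative: "In the instance of any unintentional inconsistencies, the above table definitions should take precedent in the analysis".

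The primary outcome in the same table is care entry: "Coded 1 if the child has become looked after at any point within 18 months of the referral".

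**The concern.** The table's sample line selects children on something that happens after referral, namely whether they went into care. That event is the primary outcome, and reducing it is the stated goal of the programme. If the programme changes care entry, it also changes who is left in the sample for secondary outcome 1, and the treated and control samples are no longer comparable by design.

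The line also defeats the purpose of the measure. Escalation to care was written into the definition of return so that it would not be missed, and the sample line takes those children out. The narrative has the sample that matches the rationale, but the precedence rule gives effect to the other one.

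Secondary outcome 1 is the sole measure for research question 2 and enters the Hochberg adjustment. The protocol also means to read the CPP-duration results alongside it, since a shorter CPP followed by a return would suggest premature closure. A distorted result here could carry over into that reading.

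**Working it through.** **Planning figure.** Inputs from the sample size table and Appendix B: 5 clusters, 6 periods, 1,700 children per cell, baseline p = 0.06, ICC 0.00722, two-sided alpha 0.05, power 0.8. I used the Hussey-Hughes variance.

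- p(1-p) = 0.0564. Cell variance = 0.0564 x (1 - 0.00722)/1,700 = 0.00003294. Between-cluster variance = 0.0564 x 0.00722 = 0.0004072.
- Design sums: U = 15, W = 55, V = 55. So 5U - W = 20, and U^2 + 30U - 6W - 5V = 225 + 450 - 330 - 275 = 70.
- Variance = 5 x 0.00003294 x (0.00003294 + 6 x 0.0004072) / (20 x 0.00003294 + 70 x 0.0004072) = 0.00001398, so SE = 0.00374.
- Detectable effect = (1.960 + 0.842) x 0.00374 = 0.01048, which rounds to the protocol's 0.0105.

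The total of 5 x 6 x 1,700 = 51,000 also reproduces. The point does not depend on these figures; they only scale it.

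**Who is removed.** The 6% rate is used as an approximation: it is an 18-month planning rate, and the exclusion has no stated window.

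- Control: 6.0%, or 60 per 1,000.
- Treated, if care entry falls by the detectable effect: 6.0% - 1.05% = 4.95%, or 49.5 per 1,000. If it rises by as much: 7.05%, or 70.5 per 1,000.
- With equal cells, 15 of the 30 cluster-periods are treated, so 25,500 children fall in each condition. Removed in total: 25,500 x (0.06 + 0.0495) = 2,792, or 25,500 x (0.06 + 0.0705) = 3,328.

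The loss therefore differs between conditions by up to 1.05 points because of the treatment itself.

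**Whether the direction of bias can be derived.** Let u be the return rate in children who would stay out of care either way, r the return rate in the 1.05% kept out of care by the programme, and q the share of care entrants who code as returns (a closed CPP before entering care). The documents give none of these.

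- Table's sample: effect = (0.94u + 0.0105r)/0.9505 - u = 0.0105(r - u)/0.9505.
- All referred children: effect = 0.0105(r - q).

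With assumed values, in percentage points:

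| u | r | q | Table's sample | All referred | Difference |
|---|---|---|---|---|---|
| 5% | 30% | 0 | +0.276 | +0.315 | -0.039 |
| 5% | 70% | 0 | +0.718 | +0.735 | -0.017 |
| 4.26% | 0 | 1/6 | -0.047 | -0.175 | +0.128 |
| 4.26% | 0 | 1 | -0.047 | -1.05 | +1.003 |

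The last two rows correspond to overall control return rates of 5% and 10%, with 20% and 60% of returns being care entries. In both, other returns are 4% of all children, so u = 4%/0.94 = 4.26%, and q = 1%/6% or 6%/6%.

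The exclusion slightly understates a rise in the first two rows and hides most of a fall in the last two. The sign of the difference depends mainly on q against u.

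**The case against.** The strongest defence is that the exclusion is narrower than it looks. With no window stated, the line could mean only that the index referral did not itself lead to care. A child who finishes a CPP and later becomes looked after would then stay in and code 1, so measure and sample would agree. It could also be deliberate: the research questions section says that some secondary populations are further restricted in the table. It might even serve the narrative's aim, because a child who goes straight into care without closing a CPP codes 0 in the full sample and so counts as a child who did not return.

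Part of this stands. The claim that the looked-after component can never be coded 1 holds on the plain reading only, and the coding of direct care entry is a real gap that removing the clause does not close. But the narrower reading still selects on an event after referral that belongs to the primary outcome, and it still contradicts the narrative's sample. If the restriction is intended, the narrative is wrong; if it is not, the precedence rule still enforces it.

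It is also fair that this is one of six secondary outcomes, and that the protocol itself urges caution in interpreting it. Those caveats limit the harm but do not resolve the conflict.

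**Conclusion.** The point holds as an internal contradiction that the precedence rule resolves in favour of the text at odds with the stated rationale. As written, the secondary outcome 1 sample is conditioned on the primary outcome event. At the planning figures the removal is about 60 per 1,000 control children against 49.5 per 1,000 treated. This assumes that the 18-month planning rate approximates the undated exclusion and that the effect equals the detectable one. The primary analysis and its power are untouched. It should be fixed, but it does not threaten the trial's main result.

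Two stronger readings are not supported:

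- A reader might infer that success on the primary outcome will produce a spurious rise in returns. With u = 5% and r = 30% to 70%, the treated rate in the table's sample does go from 5.00% to 5.28%-5.72%. But with q = 0 the full sample also rises, from 4.70% to 5.02%-5.44%, so that rise is not created by the exclusion. Other assumptions give attenuation of a benefit. Direction and size cannot be settled from the documents.
- A reader might extend the criticism to secondary outcomes 4 and 5, for instance to "Children aged 0-12 that have been referred within the trial period and that started pre-proceedings within 18 months of the referral". Those restrictions are deliberate: research question 4 is itself about cases already in pre-proceedings, and the Conditions section and the outcome narratives give reasons for both populations. Unconditional versions would answer different questions.

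**What to change.** Delete the last five words of the secondary outcome 1 sample line in the RCT Design Table, so that all referred children aged 0-12 are analysed as the narrative states. Add one sentence to the measure saying how a child who enters care without having closed a CPP is coded. The comparison of r with q above shows that this choice can move the result even in the full sample.

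If the authors do want to set aside children whose index referral led straight to care, they should say so in both places, give the time window, and acknowledge that the sample is then selected on an event after referral.

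The cost is a wording change made before outcome data are obtained. It needs no new data, because care entry is already collected for the primary outcome and for this measure. Secondary outcomes 4 and 5 and the Hochberg procedure stay as they are.

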### **Whether or not the child proceeds to care proceedings**

To answer research question 4, we will use a binary outcome measure indicating whether a child that enters pre-proceedings (under the PLO) continues to care proceedings within 16 weeks of the first pre-proceedings meeting. Our sample will include any child (aged 0-12 at the point of referral) that has been referred within the trial period, and then be further restricted to those that have started pre-proceedings within 18 months of the referral start date.

This outcome will measure whether Family Safeguarding reduces the rate of escalations following pre-proceedings. Family Safeguarding teams work intensively with families during pre-proceedings, and some families' main interaction with the team might occur only when the case gets to this stage. This measure will thus assess whether the impact of the programme on children at the edge of care is particularly strong.

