## **Data handling**

### **Data gathering**

Data will be collected directly from local authorities. We limit ourselves to asking for administrative data that has to be recorded for statutory returns so that our analysis will not need further data collection.

Data	Collection Point	Source
Individual-level administrative data on the sample populations (including treatment condition, and individual covariates)	In twelve month intervals, starting after the first 12 months of the trial period until the end of the trial period (six months after the last implementation date)	Directly from local authorities
Individual-level administrative data on outcome measures	In 18 month intervals, starting at the end of the trial period until 36 months after the trial period (42 months after the last implementation date)	Directly from local authorities

Local-authority level administrative data (summary statistics of the previous six months) 	In six month intervals, starting at the end of the baseline period (the date the first local authority goes Operationally Live) until the end of the trial period (six months after the last implementation date)	Directly from local authorities
---	---	---------------------------------

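### Secondary outcome 4 counts care proceedings only to week 16, so on its own it cannot separate delayed from prevented proceedings

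*Protocol*

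**What the plan says.** The RCT Design Table (Design) names the variable "Whether or not the child proceeds to care proceedings". The measure is 1 if proceedings start "within 16 weeks of the first pre-proceedings meeting, and coded 0 if not". The sample is children aged 0-12 referred in the trial period who begin pre-proceedings within 18 months of referral.

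The outcome section repeats the window ("continues to care proceedings within 16 weeks of the first pre-proceedings meeting") and then gives the purpose: "This outcome will measure whether Family Safeguarding reduces the rate of escalations following pre-proceedings".

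Research question 4 asks about the "likelihood of a case progressing from pre-proceedings (under the PLO) to care proceedings", with no time limit.

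Under Secondary Analysis, the 0/1 code goes into the same logistic mixed model as the primary outcome. Neither Sensitivity Analysis nor Regression specifications names another window or a time-to-proceedings analysis for this outcome. Data gathering schedules individual outcome data until 36 months after the trial period. No reason for 16 weeks is given.

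**The concern.** A child whose proceedings start just after week 16 and a child who never reaches proceedings get the same code. A lower 16-week rate can therefore mean fewer cases, later cases, or both. The stated purpose names only the first.

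The distinction matters because the intervention acts while the clock runs: "Family Safeguarding teams work intensively with families during pre-proceedings". Elsewhere the protocol takes seriously that the model may change durations. It fixes the time origin of the return-to-services outcome partly because the length of child protection plans may change, and it warns that changes in plan length are ambiguous. The same care is not applied to outcome 4.

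At stake is the answer to research question 4. It could be reported as fewer cases escalating when the same number escalate later. The Cost Benefit Analysis section leaves room to gauge savings in other measured areas, so the misreading could carry over there.

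**Working it through.** The protocol gives no expected rate, no time distribution and no power figure for this outcome, so there is no figure of its own to reproduce. Its one power figure (MDES 0.0105) concerns the primary outcome and has no bearing here.

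**1. What is certain.** The window is 16 × 7 = 112 days, about 3.7 months. Any start after day 112 is coded 0. This needs no assumption.

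**2. What follow-up the plan supports.** The latest referral is at the end of the trial period, pre-proceedings may begin up to 18 months later, and outcome data run to 36 months after the trial period. Taking the start of pre-proceedings as the first meeting, every child has at least 36 − 18 = 18 months (about 78 weeks) after it. The data do not force the 16-week cut.

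**3. Illustration of pure delay (all inputs assumed).** Let π be the share that eventually progresses, equal in both conditions, with exponential times of mean μ weeks. The share coded 1 by week t is π × (1 − exp(−t/μ)). With π = 0.5:

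| Counted to week | μ = 12 | μ = 20 | Gap |
|---|---|---|---|
| 16 | 0.368 | 0.275 | 9.3 points |
| 52 | 0.493 | 0.463 | 3.1 points |
| 78 | 0.499 | 0.490 | 0.9 points |

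For week 16: 0.5 × (1 − exp(−16/12)) = 0.368 and 0.5 × (1 − exp(−16/20)) = 0.275. No case is prevented in this example. Gaps are taken before rounding.

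**4. Range.** The same calculation with medians M in place of means, π × (1 − 2^(−t/M)), for π from 0.3 to 0.6:

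| Median, weeks (control v model) | Gap at week 16 | Gap at week 78 |
|---|---|---|
| 12 v 16 | 3.1 to 6.2 points | 0.7 to 1.4 points |
| 12 v 20 | 5.3 to 10.6 points | 1.7 to 3.4 points |
| 12 v 26 | 7.7 to 15.4 points | 3.4 to 6.8 points |
| 20 v 30 | 3.5 to 7.0 points | 2.9 to 5.9 points |

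The longer window shrinks the false reduction but does not remove it, and helps little where times are long (last row).

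**5. What a longer window costs in this design.** Condition is fixed at referral. Control time in the five authorities is 6, 12, 18, 24 and 30 months, 90 in total. Assume even referrals and a fixed lag L (months) from referral to first meeting. For a window of w months, the share of control referral-months whose window runs past go-live is Σ min(control time, L + w) / 90.

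| L | w = 3.68 (16 weeks) | w = 18 |
|---|---|---|
| 0 | 5 × 3.68 / 90 = 20% | (6+12+18+18+18) / 90 = 80% |
| 6 | (6 + 4 × 9.68) / 90 = 50% | (6+12+18+24+24) / 90 = 93% |
| 12 | (6+12 + 3 × 15.68) / 90 = 72% | 90 / 90 = 100% |

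The Conditions section already says that later contact of control children with the model can bias the estimate downwards.

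**The case against.** The case for leaving the plan alone is substantial.

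- *The passages agree.* The table and the outcome section give the same window, and the sentence on escalation follows that definition. Research questions 1, 2 and 5 also carry no time limit, and Outcome measures gives the table precedence. This stands: there is no internal contradiction, only a measure narrower than the conclusion drawn from it.
- *Delay is not documented.* A reader might infer that the model works longer with families, so the outcome is bound to favour it. The documents do not support that. They describe intensive work and a structured programme, not a longer phase. Earlier decisions are equally possible and would distort the result the other way. The sizes above are illustrations, not estimates for this trial.
- *Some protection exists.* The closing part of the outcome section warns against reading any single result in isolation and commits to reading results together and with the process evaluation. That caution is stressed for research questions 2 and 3, but not confined to them. The outcome 4 sample is a subset of the primary sample, so a delayed case that becomes looked after within 18 months of referral still counts in the primary outcome. The check is partial, because pre-proceedings may begin as late as month 18.
- *A short window keeps contamination down.* A reader might conclude that 16 weeks should give way to 18 months. Step 5 shows why that does not follow: the longer window runs past go-live for most control referral-months.

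These points limit the claim and rule out replacing the outcome. They do not restore the missing distinction between delay and prevention, which no planned analysis supplies.

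**Conclusion.** The point holds in a limited form. As coded, secondary outcome 4 answers whether proceedings start within 16 weeks of the first meeting. It cannot by itself support a statement that fewer cases escalate. That part follows from the definition alone.

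How far the result would mislead is unknown. The 9.3-point false reduction at week 16, against 0.9 points at week 78, rests on an assumed 50% eventual progression in both conditions, exponential times and a mean lengthening from 12 to 20 weeks. Other assumed inputs give roughly 3 to 15 points at week 16.

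This is one of six secondary outcomes, and the primary conclusion is unaffected. It is a cheap improvement that changes what may be concluded on research question 4.

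**What to change.** 1. Keep the 16-week measure as secondary outcome 4.
2. In research question 4, the outcome section and the report, state the conclusion as care proceedings within 16 weeks of the first pre-proceedings meeting.
3. Prespecify two supporting analyses: proceedings started within 18 months of the first meeting, with the same model, and the time from first meeting to proceedings by condition.
4. Claim prevention only if the reduction persists in the longer window. Persistence is necessary but not proof, since slow delay can leave a gap at 78 weeks. A reduction that fades may reflect later exposure of control children as well as delay. The time-to-proceedings summary helps with both readings.

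Cost: some wording, a little more analysis, and a check that the extract carries the dates of the first meeting and of the start of proceedings, not only a 16-week flag. The planned collection to 36 months after the trial period covers the 18-month window, so no later extract is needed. The downside is the dilution in step 5, which is why the longer window should support the 16-week outcome and not replace it.
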